On the evening of each of Treatment Periods 2-5, Day -1 (27 ± 1 days from prior dosing) subjects will self-administer fexofenadine 180 mg orally. On the morning of Treatment Period 2, Day 0, subjects will report to the clinic for the dosing of study drug. 2 hours prior to the dosing of study drug SEL-110, the subject will receive fexofenadine 180 mg orally and 1 hour prior to the dosing of study drug SEL-110, subjects will receive methylprednisolone 40 mg (or equivalent drug) intravenously. Eligible subjects who have been assigned to Cohorts 13, 15 and 17 will receive a single IV infusion of SEL-110 (dose based on a mg/kg basis) administered with a syringe infusion pump. The rate of SEL-110 infusion will be 5.5 mL/hour for the first 30 minutes and, then, will be changed to a steady rate sufficient to deliver the remainder of the dose volume for the additional 25 minutes, concurrently with a 60 minute infusion of 125 mL of normal saline. This will be followed (± 3 minutes) by an infusion delivered by infusion pump of 0.2 mg/kg SEL-037 diluted into 100 mL of normal saline delivered over 60 minutes (± 2 minutes). If necessary the infusion time may be extended in order to ensure the infusion of the study medication in entirety. Subjects will remain in the clinic for 9 hours after the start of the infusion of SEL-110 for safety evaluations and PK blood draws (see Schedule of Events below). Subjects will return for PK and PD on Days 1, 7, 14 and 21 of each treatment period and will return for safety and Antibody blood draws on Days 7, 14 and 21 of each treatment period.

1008142

SELECTA Biosciences

SEL - 212/201

SAP Version: Final 2.0

Statistical Analysis Plan

Table 2: Schedule of Events, Cohorts 1 & 2, Part B - Treatment Periods 4-5

Cohorts 1 & 2 Phases:	Out patient	In Clinic										Outpatient Follow-up Visits					
	V21	V22										V23	V24	V25	V26	Early Term	
Treatment Period #4; Visit (V); Day (D); Period (P)	P4 D-1	P4 D0 ⁸ (28 days after P3 D0)										P4 D1	P4 D7	P4 D14	P4 D21		Early Term / EOS P5 D30 ^{8,10}
Treatment Period #5; Visit (V); Day (D); Period (P)	V27	V28										V29	V30	V31	V32	P5 D21 to D30	
	P5 D-1	P5 D0 ⁸ (28 days after P4 D0)										P5 D1	P5 D7	P5 D14	P5 D21		
Hour (h)	Pre-dose	Infusion (time after dosing started)				Post-infusion (time after dosing started)						PK at ±2h from D0 0h ⁹	PK blood draws should occur at same time each visit ± 8 h from D0 0 hour ⁹				
		0h	0.25h	0.5h	0.75h	1h	1.5h	2h	3h	6h	9h						
Informed Consent																	
Dual Energy CT Scan																X	
Inflammatory Markers																X	
T-Cell Recall												X ¹¹					
Demographics																	
Inclusion/exclusion	X																
Medical History ¹	X																
Safety Examinations		Pre-dose	0h	0.25h	0.5h	0.75h	1h	1.5h	2h	3h	6h	9h					
Physical Examination																X	
Concomitant medications		← continuous →															
Vital signs ²		X	X	X	X	X	X	X	X	X	X	X	X	X	X	X	
EKG ³		X														X	
Adverse Events - Rheumatology CTC																	
Safety Labs		Pre-dose	0h	0.25h	0.5h	0.75h	1h	1.5h	2h	3h	6h	9h					
Safety Labs - As indicated in individual schedules ⁴		X												X		X	
Immunogenicity																	
Anti-Pegsiticase		X											X	X	X	X	
Anti-Uricase		X											X	X	X	X	
Anti-PEG		X											X	X	X	X	
PK/PD Assessments																	
SEL-110 PK																	
SEL-037 PK		X											X	X	X	X	
Uricase Activity		X		X		X	X	X	X	X	X		X	X	X	X	
Uric Acid		X		X		X	X	X	X	X	X		X	X	X	X	
Study Treatment		Pre-dose	0h	0.25h	0.5h	0.75h	1h	1.5h	2h	3h	6h	9h					
Study drug IV (SEL-037) : 0-60min			IV SEL-037														
Premedicate against Gout Flare ⁵																	
Premedicate against infusion reaction ⁶		X(-12h)	X(-2h)														
Premedicate against infusion reaction ⁷		X(-1h)															

1 - Confirm no active vaccinations
 2 - Blood pressure after sitting 5 minutes, heart rate, oral temperature, respiratory rate
 3 - If a conflict occurs due to multiple assessments occurring at the same time point, the ECG may be performed +/- 30 minutes from the designated time
 4 - All Safety Labs indicated in individual schedule by cohort
 5 - Premedicate with colchicine 0.6 mg QD beginning at D-7 for duration of study
 6 - Premedicate with fexofenadine at -12h ± 2h and -2h ± 1h prior to dose
 7 - Additionally premedicate with IV methylprednisolone at -1h ± 0.5h
 8 - Window for visit is +/- 1 day
 9 - Blood work as subset of listed points per schedules in Appendices by cohort
 10 - DECT and Inflammatory markers at EOS unless done at previous P5 visit
 11 - T-Cell recall sample ONLY for Treatment Period 5 (Visit 30) only

1008142

SELECTA Biosciences

SEL - 212/201

SAP Version: Final 2.0

Statistical Analysis Plan

Table 3: Schedule of Events, Cohorts 3-8, 10, 11, and 12, Part A - Treatment Periods 1-3

Cohorts 3 - 8, 10, 11, & 12	Phases:	Screen	Outpatient Visits			In Clinic									Outpatient Follow-up Visits									
		V1 D-45 to -1	V2 ¹¹ P1 D-7	V3 P1 D-1	V4 P1 D0	V5 P1 D1	V6 P1 D7	V7 P1 D14	V8 P1 D21	V9 P2 D-1	V10 P2 D0 ⁸ (28 days after P1 D0)	V11 P2 D1	V12 P2 D7	V13 P2 D14	V14 P2 D21	V15 P3 D-1	V16 P3 D0 ⁸ (28 days after P2 D0)	V17 P3 D1	V18 P3 D7	V19 P3 D14	V20 P3 D21	Early Term		
Hour (h)				Pre-dose	0h	0.25h	0.5h	0.75h	1h	1.5h	2h	3h	6h	9h	PK at ±2h from D0 0h ⁹	PK blood draws should occur at same time each visit ± 8 h from D00 hour ⁹								
Informed Consent	X																							
Dual Energy CT Scan	X																						X ¹⁵	X
Inflammatory Markers				X ¹²																				X
T-Cell Recall				X ¹²																				X
Demographics	X																							
Inclusion/exclusion	X		X																					
Medical History ¹	X																							
Safety Examinations					Pre-dose	0h	0.25h	0.5h	0.75h	1h	1.5h	2h	3h	6h	9h									
Physical Examination	X																							X
Concomitant medications																								
Vital signs ²	X			X	X	X	X	X	X	X	X	X	X	X	X	X	X	X	X	X	X	X	X	X
Weight	X																						X	
ECG ³	X			X										X ¹³										X
Adverse Events - Rheumatology CTC																								
Safety Labs					Pre-dose	0h	0.25h	0.5h	0.75h	1h	1.5h	2h	3h	6h	9h								X	X
Safety Labs - As Indicated in Individual schedules ⁴	X			X																		X	X	X
Immunogenicity																							X	X
Anti-Pepsitc case				X																		X	X	X
Anti-Uricase				X																		X	X	X
Anti-PEG	X			X																		X	X	X
PK/PD Assessments																								
SEL-110 PK				X	X	X	X	X	X	X	X	X	X	X	X	X	X	X	X	X	X	X	X	X
SEL-037 PK				X																		X	X	X
Uricase Activity				X					X	X	X	X	X	X	X	X	X	X	X	X	X	X	X	X
Uric Acid	X			X					X	X	X	X	X	X	X	X	X	X	X	X	X	X	X	X
Study Treatment					Pre-dose	0h	0.25h	0.5h	0.75h	1h	1.5h	2h	3h	6h	9h									
Study drug IV (SEL-110) : 0-55min ¹⁴																								
Study drug IV (SEL-037) : 60-120 min																								
Premedicate against Gout Flare ⁵			X																					
Premedicate against infusion reaction ⁶				X(-12h)	X(-2h)																			
Premedicate against infusion reaction ⁷					X(-1h)																			

1 - Confirm no active vaccinations
2 - Blood pressure after sitting 5 minutes, heart rate, oral temperature, respiratory rate
3 - If a conflict occurs due to multiple assessments occurring at the same time point, the ECG may be performed +/- 30 minutes from the designated time
4 - All Safety Labs indicated in individual schedule by cohort
5 - Premedicate with colchicine 0.6 mg QD beginning at D-7 for duration of study
6 - Premedicate with fexofenadine at -12h ± 2h and -2h ± 1h prior to dose
7 - Additionally premedicate with IV methylprednisolone at -1h ± 0.5h
8 - Window for visit is +/- 1 day
9 - Blood work as subset of listed points per schedules in Appendices by cohort
10 - ECG at 6 hr ONLY for Treatment Period 1, not for Treatment Periods 2 nor 3
11 - Gout flare premedication can be started during screening interval and does not require an on-site visit
12 - T-Cell recall sample and Inflammatory marker sample ONLY for Treatment Period 1 (Visit 4) only
13 - T-Cell recall sample ONLY for Treatment Period 3 (Visit 18) only
14 - In cohorts receiving SEL-110 doses <0.10 mg/kg, SEL-110 will be infused at a single steady rate sufficient to deliver the dose volume over a period of 55 minutes concurrently with a 60 minute infusion of 125 mL of normal saline. In cohorts receiving ≥0.10 mg/kg SEL-110, the rate of SEL-110 infusion will be 5.5 mL/hour for the first 30 minutes and, then, will be changed to a steady rate sufficient to deliver the remainder of the dose volume for the additional 25 minutes, concurrently with a 60 minute infusion of 125 mL of normal saline.
15 - DECT is permitted to be performed at any time between Days 21-28 (inclusive) of Treatment Period 3.

Note: Cohorts 9 is intentionally omitted from the protocol in order to maintain the cohort numbering convention of associating even numbered cohorts with the 0.4 mg/kg SEL-037 dose.

Statistical Analysis Plan

Table 4: Schedule of Events, Cohorts 3-8, 10, 11, and 12, Part B - Treatment Periods 4-5

Cohorts 3 - 8, 10, 11, & 12	Phases:	Out patient	In Clinic										Outpatient Follow-up Visits				
		V21	V22										V23	V24	V25	V26	Early Term
Treatment #4; Visit (V); Day (D)	P4 D-1	P4 D-1	P4 D0 ⁸ (28 days after P3 D0)										P4 D1	P4 D7	P4 D14	P4 D21	
Treatment #5; Visit (V); Day (D)	P5 D-1	P5 D-1	P5 D0 ⁸ (28 days after P4 D0)										P5 D1	P5 D7	P5 D14	P5 D21	
Hour (h)		Pre-dose	Infusion (time after dosing started)				Post-infusion (time after dosing started)					PK at ±2h from D0 0h ⁸	PK blood draws should occur at same time each visit ± 8 h from D0 0 hour ⁸				
			0h	0.25h	0.5h	0.75h	1h	1.5h	2h	3h	6h	9h					
Informed Consent																	
T-Cell Recall													X ¹²			X	
Dual Energy CT Scan																X	
Inflammatory Markers																X	
Demographics																	
Inclusion/exclusion		X															
Medical History ¹		X															
Safety Examinations		Pre-dose	0h	0.25h	0.5h	0.75h	1h	1.5h	2h	3h	6h	9h					
Physical Examination																X	
Concomitant medications			←----- continuous ----->														
Vital signs ²		X	X	X	X	X	X	X	X	X	X	X	X	X	X	X	
Weight															X		
ECG ³		X														X	
Adverse Events - Rheumatology CTC			←----- continuous ----->														
Safety Labs		Pre-dose	0h	0.25h	0.5h	0.75h	1h	1.5h	2h	3h	6h	9h					
Safety Labs - As indicated in individual schedules ⁴		X												X	X	X	
Immunogenicity																	
Anti-Pegsiticase		X												X	X	X	
Anti-Uricase		X												X	X	X	
Anti-PEG		X												X	X	X	
PK/PD Assessments																	
SEL-110 PK		X ¹¹														X	
SEL-037 PK		X											X	X	X	X	
Uricase Activity		X		X		X	X	X	X	X	X	X	X	X	X	X	
Uric Acid		X		X		X	X	X	X	X	X	X	X	X	X	X	
Study Treatment		Pre-dose	0h	0.25h	0.5h	0.75h	1h	1.5h	2h	3h	6h	9h					
Study drug IV (SEL-037) : 0-60min			IV SEL-037														
Premedicate against Gout Flare ⁵																	
Premedicate against infusion reaction ⁶		X(-12h)	X(-2h)														
Premedicate against infusion reaction ⁷		X(-1h)	X(-1h)														

1 - Confirm no active vaccinations
 2 - Blood pressure after sitting 5 minutes, heart rate, oral temperature, respiratory rate
 3 - If a conflict occurs due to multiple assessments occurring at the same time point, the ECG may be performed +/- 30 minutes from the designated time
 4 - All Safety Labs indicated in individual schedule by cohort
 5 - Premedicate with colchicine 0.6 mg QD beginning at D-7 for duration of study
 6 - Premedicate with fexofenadine at -12h ± 2h and -2h ± 1h prior to dose
 7 - Additionally premedicate with IV methylprednisolone at -1h ± 0.5h
 8 - Window for visit is +/- 1 day
 9 - Blood work as subset of listed points per schedules in Appendices by cohort
 10 - DECT and Inflammatory markers at EOS unless done at previous P5 visit
 11 - Pre-dose sample collected on Treatment Period 4 only
 12 - T-Cell recall sample ONLY for Treatment Period 5 (Visit 30) only
 13 - Additional observational visit at Treatment Period 5, Day 60 may be required as per section 10.1.1

Note: Cohorts 9 is intentionally omitted from the protocol in order to maintain the cohort numbering convention of associating even numbered cohorts with the 0.4 mg/kg SEL-037 dose.

4. ENDPOINTS

4.1. PHARMACOKINETIC ENDPOINTS

The following PK parameters will be calculated on SEL-037 and SEL-110 (rapamycin) PK concentration as well as uricase activity separately for each analyte and type of PK assessment using noncompartmental intravascular infusion log-linear model for each Cohort and Treatment Period where possible and summarized statistically:

C_{max}	Maximum observed PK concentration or activity
T_{max}	Time of maximum observed PK concentration or activity
C_{last}	Last observed PK concentration or activity
T_{llast}	Time of last observed PK concentration or activity
AUC_{0-last}	Area under the serum concentration-time curve from time zero to the time of the last quantifiable PK concentration or activity
AUC_{0-inf}	Area under the PK concentration or activity-time curve from time zero extrapolated to infinity
$t_{1/2}$	Terminal elimination half-life
λ_z	Terminal elimination rate constant
CL	Clearance of drug
V_d	Terminal volume of distribution

Additional PK parameters may be calculated as needed. Change from baseline in uricase activity may be used for derivation of PK parameters in addition to actual measured activity.

Multiple dose parameters will be also derived where possible:

C_{min}	Min observed trough PK concentration or activity
T_{min}	Time of min observed PK concentration or activity
C_{ave}	Average observed PK concentration or activity
AUC_{τ}	Area under the PK concentration or activity from time 0 to the end of dosing interval
% Fluctuation	Difference between C_{max} and C_{min} normalized by average concentration
$R_{AUC\tau}$	Accumulation ratio based on comparison of AUC_{τ} between last and first dose
$R_{C_{max}}$	Accumulation ratio based on comparison of C_{max} between last and first dose
$R_{C_{min}}$	Accumulation ratio based on comparison of C_{min} between last and first dose
CL_{ss}	Steady state clearance (if steady state is achieved)

Statistical Analysis Plan

4.2. PHARMACODYNAMIC ENDPOINTS

The following PD parameters will be calculated on PD uric acid for each Cohort and Treatment period and Overall where possible. The parameters will be derived for actual measurements of uric acid as well as for % change from baseline:

C_{min}	Minimal observed serum concentration
T_{min}	Time of minimal observed serum concentration
CFB_{min}	Minimum observed change from baseline in serum concentration
$AUE_{CFBlast}$	Absolute value for Area under the change from baseline in effect-time curve from time zero to the time of the last quantifiable concentration (effect - uric concentration)
$TA_{AUE_{CFBlast}}$	Time adjusted area under the absolute value for effect-time curve from time zero to the time of last quantifiable concentration (effect - uric concentration)
T_{onset}	Time of onset of effect - first time point of reduction uric acid concentration >10% of baseline
$T_{resolve}$	Time of resolution of effect - first time point of return of uric acid concentration to baseline defined as <10% difference from pre-dose baseline
$T_{duration}$	Time of duration of effect, calculated as $T_{resolve} - T_{onset}$

4.3. SAFETY ENDPOINTS

The primary objective of this study is to assess the safety and tolerability of multiple IV infusions of SEL-212. Safety assessments will be based on medical review of adverse event (AE) reports and the results of vital sign measurements, electrocardiograms (ECGs), physical examinations, and clinical laboratory tests. These endpoints will be measured at the time points specified in the protocol in Section 1.1, Schedules of Events. The primary endpoints are frequencies of AEs, serious AEs (SAEs), AEs leading to discontinuation, and ECG and laboratory abnormalities occurring up to 30 days after the last dose of study medication.

4.4. IMMUNOGENICITY ENDPOINTS

Immunogenicity endpoints include occurrence of anti-PEG, anti-pegsiticase, and anti-uricase specific antibodies based on screening assay; and the titer for the anti-pegsiticase antibodies, where the confirmation assay is also available. Frequency of occurrence of antibodies by study day and overall by cohort, time of onset immunogenicity, and time of resolution of immunogenicity will be calculated and summarized by treatment in summary tables. Time of onset is defined as the first time point with positive ADA (anti-drug antibodies) result; time of resolution is defined as the

1008142

SELECTA Biosciences

SEL - 212/201

SAP Version: Final 2.0

Statistical Analysis Plan

first time point when a previously observed positive ADA result returns to baseline. Titers of antibodies against PEG, uricase and pegsiticase will be listed.

Statistical Analysis Plan

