10. ANALYSIS OF IMMUNOGENICITY

Immunogenicity endpoints include screening and confirmation results for IgG antibodies to pegsiticase, uricase, and IgM anti-PEG antibody. The titer for the anti-pegsiticase IgG antibodies will be determined during confirmation assay. The titer for the anti-uricase IgGs will be reported for positive samples. Preliminary concentration for anti-PEG IgM will be estimated in screening assay and confirmed in confirmation assay using multiple dilutions.

The Parts A/B (Treatment periods 1-3 and 4-5 for cohorts 1-8, 10-12 respectively) will be presented together separately from Part C (cohorts 13, 15) unless necessary for comparative analysis.

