10.4. DATA PRESENTATION FOR IMMUNOGENICITY

Immunogenicity sampling times and results will be listed for safety analysis set outlined in Section 5.2 in this SAP. Immunogenicity endpoints include occurrence of anti-PEG, anti-pegsiticase, and anti-uricase specific antibodies based on screening assay and the titer for the anti-drug antibodies as identified in the confirmation assay.

Frequency of occurrence of antibodies by study day and overall by cohort, time of onset immunogenicity and time of resolution of immunogenicity will be calculated and summarized by treatment in summary tables. Time of onset is defined as 1st time point with positive ADA result; time of resolution is defined as 1st time point when previously observed positive ADA result returns to baseline. Titer of antibodies against PEG, uricase and pegsiticase will be listed. The effect of possible antibody responses on PK and PD parameters will be evaluated descriptively.

Cumulative positive ADA result for subject will be defined for each treatment period separately as at least one positive antibody post-dose time point for each Treatment period and Overall. The ADA positive subjects will be also stratified by the titer values for anti-pegsiticase and anti-uricase. The limits for titer values for low, moderate and high range will be identified based on percentiles after review of actual data (for example ≤ 30 percentile - low, 31-70 percentile - moderate, 71-100 percentile - high). Cumulative negative result will be defined as negative ADA result at all time points for a subject during each Treatment period.

Following tables will be produced to evaluate effect of immunogenicity on PK:

Statistical Analysis Plan

- Descriptive statistics of the key PD parameters based on measured values and $\%CFB$, $\%CFB_{\min}$, $AUE_{\%CFBlast}$, and $TA_AUE_{\%CFBlast}$ as well as uric acid concentration and $\%CFB$ on day 21 of each treatment period for ADA positive and negative, ADA low, moderate and high titer groups including Q1, Q3, 5, 10, 90 and 95 percentiles. The data will be presented by cohort and overall.
- Descriptive statistics of the key PK parameters based on measured values and C_{\max} , T_{\max} , AUC_{0-last} , and AUC_{0-inf} for ADA positive and negative, ADA low, moderate and high titer groups including Q1, Q3, 5, 10, 90 and 95 percentiles. The data will be presented by cohort and overall.

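### SAP 4.4 and 10.4 base ADA occurrence on the screening assay with no baseline condition, in conflict with SAP 10, so unconfirmed or pre-existing reactivity can count as positive

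*SAP*

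**What the plan says.** Two sections of the SAP state an occurrence rule, and both name the screening assay. Section 4.4 does so for all three antibodies: "Immunogenicity endpoints include occurrence of anti-PEG, anti-pegsiticase, and anti-uricase specific antibodies based on screening assay". It gives confirmation a narrower role: "the titer for the anti-pegsiticase antibodies, where the confirmation assay is also available". Section 10.4 has the same split: "specific antibodies based on screening assay and the titer for the anti-drug antibodies as identified in the confirmation assay".

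The opening of SAP 10 reads differently: "Immunogenicity endpoints include screening and confirmation results for IgG antibodies to pegsiticase, uricase, and IgM anti-PEG antibody". For anti-PEG it adds: "Preliminary concentration for anti-PEG IgM will be estimated in screening assay and confirmed in confirmation assay using multiple dilutions".

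At subject level, SAP 10.4 defines a cumulative positive as "at least one positive antibody post-dose time point for each Treatment period and Overall". A cumulative negative needs negative results at every time point of the period. On onset it says: "Time of onset is defined as 1st time point with positive ADA result". Baseline enters only the definition of resolution, which is a return to baseline. No treatment-emergent category (induced or boosted) is defined for ADA.

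**The concern.** Whether SEL-212 prevents antibodies to uricase and pegsiticase is a stated purpose of the study (SAP 3.4), and immunogenicity is a secondary objective. The same ADA status feeds the frequency and onset tables (SAP 10.3), the ADA-positive versus ADA-negative PK and PD tables (SAP 10.4 and 10.5), and a possible covariate in the PD model (SAP 10.4). A programmer following 4.4 or 10.4 would count a sample that screened positive and was not confirmed. The same programmer would count a subject who was already reactive before the first infusion and stayed so.

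Sample number adds a second problem. In the SEL-212 cohorts a subject continues only if serum uric acid is at or below 1.0 mg/dL at Day 21 (Protocol 6.3.1), so uric-acid responders give the most samples. Under an any-positive rule they have the most chances of a false positive. Cohorts have 6 to 20 subjects, so a few misclassified subjects can change the picture.

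**Working it through.** The plan gives no ADA rate, screening cut-point or baseline prevalence, so there is no figure of its own to reproduce. The check has three parts.

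**1. Which tier decides.** SAP 4.4 and 10.4 use screening for occurrence and confirmation for titer. SAP 10 makes confirmation results endpoints for all three antibodies. None of them says how to classify a sample that screens positive and fails confirmation. The sections conflict, and the only explicit occurrence rule points to screening.

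**2. Baseline.** Pre-dose samples are collected in every period, and Day 0 is in the schedule of SAP 10.1. Neither cumulative positivity nor onset refers to the pre-dose result. Read literally, onset for a baseline-positive subject falls before dosing. A subject who is positive pre-dose and negative afterwards fits neither cumulative class if Day 0 counts as a time point of the period.

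The effect on the reported rate can be sketched with assumed values. Let b be the baseline prevalence, t the induced rate among baseline negatives, and suppose baseline positives stay positive. The SAP rule reports b + (1 − b)t and a treatment-emergent rule reports (1 − b)t, so the excess is b. With t = 30%:
- b = 2%: 31.4% versus 29.4%
- b = 5%: 33.5% versus 28.5%
- b = 10%: 37.0% versus 27.0%

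**3. Accumulation in the Overall flag.** Let f be an assumed false-positive rate per sample and k the number of post-dose samples from a truly negative subject. With independent samples, P(at least one positive) = 1 − (1 − f)^k. With perfect within-subject correlation it is f for any k. The counts come from the documents:
- Period 1 stop: Days 7, 14, 21 and the final visit, k = 4.
- Completer, minimum set guaranteed for analysis by Protocol 10.2: Day 14 and the next pre-dose sample in Periods 1 to 4 (8), plus Days 7, 14, 21 and end of study in Period 5 (4), k = 12.
- Completer, every sample assayed: 15 from Days 7, 14 and 21 over five periods, four later pre-doses and end of study, k = 20.

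| Assumed f | Perfect correlation, any k | k = 4 | k = 12 | k = 20 |
|---|---|---|---|---|
| 1% | 1% | 3.9% | 11.4% | 18.2% |
| 5% | 5% | 18.5% | 46.0% | 64.2% |
| 10% | 10% | 34.4% | 71.8% | 87.8% |

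The last three columns are upper values. For 20 truly negative completers at f = 5%, the expected number falsely flagged per antibody is 20 × 0.05 = 1.0 at the lower end. At the upper end it is 20 × 0.460 = 9.2 with 12 samples or 20 × 0.642 = 12.8 with 20. The gap between a completer and a Period 1 stop is zero under perfect correlation. Under independence it is 46.0 − 18.5 = 27.5 points with 12 samples and 64.2 − 18.5 = 45.7 points with 20.

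**After the change.** If confirmation wrongly passes 1% to 5% of false screening positives (assumed), the per-sample rate at f = 5% becomes 0.05% to 0.25%. The 20-sample upper value then falls from 64.2% to between 1.0% and 4.9%.

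**The case against.** Confirmation and baseline are not disregarded. SAP 10 names confirmation results as endpoints, and titers are tied to the confirmation assay. Baseline is defined in SAP 6.2, ADA is sampled pre-dose, and resolution is judged against baseline. Entry requires a negative anti-PEG result and no earlier uricase exposure (Protocol 7.1 and 7.2). Tables by study day that include Day 0 would show baseline positives. Accumulation affects the Overall flag only: SAP 10.4 also classifies by period, SAP 10.3 tabulates by time point, and the cross-table against the uric-acid stopping rule is time-matched at Day 21. The ADA subgroup comparisons carry no statistical inference (SAP 10.5), and the PD model with an ADA covariate is optional.

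Most of this stands and limits the point. It does not supply a rule for an unconfirmed positive or a baseline condition for positivity and onset. The entry criteria test only anti-PEG. Excluding earlier uricase exposure does not remove cross-reactivity, which Protocol 4.4.1 itself offers as a presumed explanation for first-dose reactions to uricases.

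A reader might infer that the SAP reports false or pre-existing positives as drug-induced. It does not: its terms are occurrence and frequency. A reader might also infer that the rule hides the SEL-110 effect. The documents support only possible dilution in the Overall flag, because the gap in false positives disappears if errors within a subject are fully correlated.

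**Conclusion.** The point holds as a conflict between SAP 4.4/10.4 and SAP 10 over the assay tier, together with a missing baseline or titer-rise condition for positivity and onset. As written, unconfirmed or pre-existing reactivity can enter the ADA frequency, onset and PK/PD subgroup tables.

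The size is unknown. At an assumed 5% per sample, the Overall false-positive rate for a completer lies between 5% and 46% on the guaranteed samples, or up to 64% if all are assayed. For a Period 1 stop it lies between 5% and 19%. The upper ends assume independent errors and should not be read as expected rates. The pre-existing component cannot be quantified, because no baseline prevalence is given.

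This should be corrected before database lock. It concerns a secondary, mainly descriptive endpoint and leaves the primary safety endpoints untouched.

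**What to change.** - State that a sample is positive only if confirmed, and align SAP 4.4 and 10.4 with SAP 10.
- Define treatment-emergent ADA as Period 1 pre-dose negative to post-dose confirmed positive, or a pre-specified titer rise over the Period 1 pre-dose value.
- Use that definition for occurrence, onset, duration and the PK/PD subgroup tables.
- Report baseline prevalence separately, and show unconfirmed screening positives in listings only.
- Base cohort comparisons on the by-period classification and not on the Overall flag.

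The cost is SAP wording and one derived variable, with no new blood samples. The proviso is anti-uricase: SAP 10 promises confirmation results for it but describes no confirmation procedure, and SAP 4.4 mentions confirmation only for anti-pegsiticase. Protocol 4.3.2.3 calls anti-uricase the most sensitive ADA measure in Phase 1, so the availability of those results should be checked first.
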